3.5 Secondary Study Endpoints

The secondary endpoints of the study are the patient outcomes in the postoperative period and 30-day mortality rate.

3.6 Primary Safety Endpoints

This is an exploratory efficacy study with no specific primary safety endpoint. Adverse events will be tracked and reported using Good Clinical Practice standards.

3.7 Identification of Source Data

The following source data will be directly recorded in the EHR and later retrieved by the study team members:

- Vital signs (including hemodynamic values)
- Intraoperative Events

• Postoperative Patient Outcomes

4 Subject Selection Enrollment and Withdrawal

4.1 Inclusion Criteria

- Age > or = 18 years old
- Patients scheduled to undergo liver transplantation
- Patients able to read and understand consent document (if patient is unable to provide an informed consent, the Legally Authorized Representative will be ask to consent on behalf of the patient).
- SVR lower than 500 dynes-sec/cm⁻⁵ sustained for more than 5 minutes despite the administration of vasopressors intraoperatively (this criterion must be met after consent intraoperatively)

4.2 Exclusion Criteria

- Patients with glucose-6-phosphate dehydrogenase (G6PD) deficiency documented as a medical history
- Patients taking serotonergic drugs such as selective serotonin reuptake inhibitors (SSRIs), serotonin and norepinephrine reuptake inhibitors (SNRIs), and monoamine oxidase inhibitors (MAOIs)
- Patients with allergy to methylene blue or hydroxocobalamin

4.3 Subject Recruitment, Enrollment and Screening

Subjects will be enrolled from the Departments of Anesthesiology and Transplantation at the Mayo Clinic in Florida. Patients will be initially approached when they are evaluated and placed on a transplant waiting list. Full discussion about the study will take place at that time and the actual written consent will not be obtained until the day of surgery. The study has an accrual target of 20 patients. In the year 2017, 150 unique patients underwent LT at Mayo Clinic in Florida and thus no difficulties in accrual based on historical volumes are anticipated. Co-departmental participation aids in reaching accrual targets and minimizing referral bias. The initial accrual period will last at least 24 months and treatment of participants may not occur for all should they not experience intraoperative refractory vasoplegia. Patients will be provided with a Research Participant Consent and Privacy Authorization Form describing the study drug, protocol, inclusion and exclusion criteria, as well as risks and benefits of participation.

4.3.1 Capacity to consent assessment

All potential subjects should be recruited and informed of the study as outlined in the study protocol. To determine whether the subject has the capacity to provide consent, the study team

member will ask the following questions at the conclusion of the consent process:

Level of Understanding 5-Point Scale

1= None, 2= Poor, 3=Unclear, 4=Good, 5=Excellent

Assessment Questions	Level (circle			lerstan	ding
Why is this study being done?	1	2	3	4	5
If you decide to participate in the study, what are some of the things you will be asked to do?	1	2	3	4	5
What parts of the study are being done as part of your regular care and what parts of the study are being done only for the research?	1	2	3	4	5
Describe some of the risks or discomforts that people may experience if they participate in this study.	1	2	3	4	5
What are the benefits of participating in this study?	1	2	3	4	5
Do you have to be in this study?	1	2	3	4	5
What will happen if you decide not to be in the study?	1	2	3	4	5
If you are in the study and stop your participation, will you still be able to receive regular care?	1	2	3	4	5
Who will pay for your medical care if you are injured while in this study?	1	2	3	4	5
Who should you contact if you have questions or experience a problem while in the study?	1	2	3	4	5

Individuals who achieve a demonstrated understanding (scoring a 4 or 5 on all questions) of the study are determined to have capacity to provide consent. However, if in answering these

questions, the potential subject is unable to demonstrate understanding, reasoning, or appreciation of the study, and the Investigator still wishes to enroll the subject, the consent should be reviewed with the Legally Authorized Representative.

Transplant team identifies the legally authorized representative at the time of patients' admission in order to obtain permission for necessary procedures/treatments. We will obtain consent for participation from a family member or legally authorized representative (LAR) proxy as recorded in the patient's medical record if an eligible patient is unable to participate in a lengthy consent process.

A member of the research team will approach the designated proxy LAR and explain the study and what is being asked of the family member if consent is provided to participate in the study. Each proxy will then read the consent form and be asked to re-phrase to a member of the research team what the study aims are, how long the patient will remain in the study, and if payment will be received. Opportunity will be provided for asking questions concerning the protocol.

If the LAR is not physically available, the participant will not be enrolled in the study and will proceed with SOC transplant surgery and medical care.

4.4 Early Withdrawal of Subjects

4.4.1 When and How to Withdraw Subjects

Patients are free to withdraw at any time and for whatever reason. No data will be collected for withdrawn subjects. Withdrawn subjects may be replaced during the accrual period. Prespecified reasons for discontinuing include, but are not limited to, the following:

- Patient Request: Patient decided that he/she did not want to continue (for any reason)
- Adverse Event: Patient experienced a related or unrelated event that would interfere with the study objectives/evaluation
- Treatment Failure: If in the Principal Investigator and/or Investigators' judgment, the patient's condition required another form of treatment
- Inclusion/Exclusion Discrepancy/Violation: Patient should not have been enrolled
- Noncompliance: Patient is not complying with the protocol requirements (i.e. visit schedule, dosing, regimen, etc.); a patient is to be withdrawn if he/she misses two consecutive visits
- Other: Any other reason

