- The risks of hydroxocobalamin: Common side effects include increased blood pressure, erythema, rash, nausea, decreased lymphocyte count, headache, and abnormal red urine color.

2 Study Objectives

Primary Objective

To assess the efficacy of hydroxocobalamin as compared to methylene blue on improving hemodynamic stability as measured by SVR, systemic blood pressure, and amount of vasopressors administered.

Secondary Objective

The secondary end point will examine the patient outcomes in the postoperative period as measured by early tracheal extubation after surgery, length of hospital and intensive care unit stay, perioperative complications (stroke, myocardial infarction, and acute renal failure), graft function, and survival rate.

3 Study Design

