4.4.2 Data Collection and Follow-up for Withdrawn Subjects

If a Participant withdraws from the study, no additional attempts will be made to contact the Participant.

5 Study Drug

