For this study, the study treatment follow-up period is defined as 90 minutes following the last administration of study treatment.

Preexisting Condition

A preexisting condition is one that is present at the start of the study. A preexisting condition should be recorded as an adverse event if the frequency, intensity, or the character of the condition worsens during the study period.

General Physical Examination Findings

At screening, any clinically significant abnormality should be recorded as a preexisting condition. At the end of the study, any new clinically significant findings/abnormalities that meet the definition of an adverse event must also be recorded and documented as an adverse event.

Post-study Adverse Event

All unresolved adverse events should be followed by the sponsor-investigator until the events are resolved, the subject is lost to follow-up, or the adverse event is otherwise explained. At the last scheduled visit, the sponsor-investigator should instruct each subject to report, to the sponsor-investigator, any subsequent event(s) that the subject, or the subject's personal physician, believes might reasonably be related to participation in this study.

Hospitalization, Prolonged Hospitalization or Surgery

Any adverse event that results in hospitalization or prolonged hospitalization should be documented and reported as a serious adverse event unless specifically instructed otherwise in this protocol. Any condition responsible for surgery should be documented as an adverse event if the condition meets the criteria for an adverse event.

Neither the condition, hospitalization, prolonged hospitalization, nor surgery are reported as an adverse event in the following circumstances:

• Hospitalization or prolonged hospitalization for therapy of the target disease of the study, unless it is a worsening or increase in frequency of hospital admissions as judged by the clinical investigator.

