8.2 Recording of Adverse Events

At each contact with the subject, the study team must seek information on adverse events by specific questioning and, as appropriate, by examination. Information on all adverse events should be recorded immediately in the source document, and also in the appropriate adverse

event section of the electronic case report form (CRF). All clearly related signs, symptoms, and abnormal diagnostic, laboratory or procedure results should recorded in the source document.

All adverse events occurring during the study period must be recorded. The clinical course of each event should be followed until resolution, stabilization, or until it has been ultimately determined that the study treatment or participation is not the probable cause. Serious adverse events that are still ongoing at the end of the study period must be followed up, to determine the final outcome. Any serious adverse event that occurs during the Adverse Event Reporting Period and is considered to be at least possibly related to the study treatment or study participation should be recorded and reported immediately.

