9.1 Confidentiality

Information about study subjects will be kept confidential and managed according to the requirements of the Health Insurance Portability and Accountability Act of 1996 (HIPAA). Those regulations require a signed subject authorization informing the subject of the following:

- What protected health information (PHI) will be collected from subjects in this study
- Who will have access to that information and why
- Who will use or disclose that information
- The rights of a research subject to revoke their authorization for use of their PHI.

In the event that a subject revokes authorization to collect or use PHI, the investigator, by regulation, retains the ability to use all information collected prior to the revocation of subject authorization. For subjects that have revoked authorization to collect or use PHI, attempts should be made to obtain permission to collect at least vital status (long term survival status that the subject is alive) at the end of their scheduled study period.

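### Section 4.4.1 stops data collection for withdrawn patients, dosed or not, and cannot be followed together with sections 7.3, 8.1 and 8.2

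*Combined protocol and SAP*

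**What the plan says.** Section 4.4.1 gives one data rule for all withdrawals: "No data will be collected for withdrawn subjects". The same paragraph permits replacement during accrual. Three of the listed reasons are the investigator's to apply:

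- adverse event: "Patient experienced a related or unrelated event that would interfere with the study objectives/evaluation"
- treatment failure, where the investigator judges that the patient needs some other treatment
- eligibility: "Inclusion/Exclusion Discrepancy/Violation: Patient should not have been enrolled"

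None distinguishes withdrawal before dosing from withdrawal after it. Section 4.4.2 adds that when a participant withdraws, "no additional attempts will be made to contact the Participant".

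Other sections assume that data on withdrawn patients exist or must be obtained:

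- Section 7.3 places all dosed participants in the primary analysis whatever their withdrawal status, and plans a sensitivity analysis that leaves out those who withdrew.
- Section 8.1: "All unresolved adverse events should be followed by the sponsor-investigator until the events are resolved", with loss to follow-up or another explanation as the other end points.
- Section 8.2 requires every adverse event in the study period to be recorded, and states "Serious adverse events that are still ongoing at the end of the study period must be followed up, to determine the final outcome".
- Section 9.1, on revoked authorization, keeps what was already collected and says "attempts should be made to obtain permission to collect at least vital status".

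The secondary objective in section 2 includes "perioperative complications (stroke, myocardial infarction, and acute renal failure), graft function, and survival rate", and section 3.5 adds 30-day mortality.

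**The concern.** The treatment is a single intraoperative dose, and section 9.3 takes all study data from the EHR. Once a patient has been dosed, withdrawal by the investigator leaves little study treatment to stop. Read as written, what it stops is data collection.

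The reasons for withdrawal are not neutral. Treatment failure is close to the opposite of the primary endpoint, and an adverse event that leads to withdrawal may itself be a secondary outcome or be followed by one. Missing data that arise this way are related to outcome. With replacement, the place of a patient who did badly can be taken by another. The study exists to supply descriptive estimates for a larger trial (section 7.1), so a rule that trims unfavourable courses undermines its main product.

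**Working it through.** The plan has no sample size calculation (section 7.1), so there is no power figure to reproduce. The allocation is consistent: 10 + 10 = 20. The check is a comparison of the text, followed by an illustration of scale.

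**1. Can the rules be followed together?** Take a dosed patient whom the investigator withdraws for treatment failure.

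- Under 4.4.1, no data are collected, or on a milder reading none after withdrawal.
- Under 7.3, the patient is in the primary analysis. That needs hemodynamic and vasopressor data, some of which may fall after withdrawal. The sensitivity analysis compares results with and without such patients, so it also needs their data.
- Under 8.1 and 8.2, an open adverse event must be followed and a serious one taken to its final outcome. Neither section exempts withdrawn patients.
- Under 7.2, missing values are not imputed. The patient is therefore in the 7.3 population but drops out of each summary for which data were not collected.

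Staff cannot comply with both 4.4.1 and the other sections. On the milder reading, later hemodynamics, complications, length of stay, 30-day mortality and adverse event outcomes are still lost.

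**2. How often might it happen?** The documents give no withdrawal rate. The only related figure is the chart review in section 1.3, where 9 of 14 methylene blue patients had an ineffective response and then received hydroxocobalamin.

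- 9/14 = 64% (exact 95% CI 35% to 87%)
- applied to an arm of 10: 10 × 9/14 = 6.4 patients

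This assumes that the review's definition of ineffective response matches the trial's, and that such patients would be classed as withdrawn. Neither is stated. There is no corresponding figure for hydroxocobalamin given first.

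**3. What does one lost patient do to an arm of 10?** The event counts below are assumed.

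- All data kept: 2/10 = 20% (exact 95% CI 2.5% to 55.6%).
- One of the two event patients lost, no replacement: 1/9 = 11%, a fall of 8.9 points.
- One lost and replaced by a patient without the event: 1/10 = 10%, a fall of 10 points.
- Every event patient lost: 1/10, 2/10 and 3/10 become 0/9, 0/8 and 0/7, so 0% is reported each time. With full replacement the arm shows 0/10, upper 95% limit 30.8%.

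**4. Is an event in an arm of 10 likely at all?** P(at least one) = 1 − (1 − p)^10. For assumed risks p of 5%, 10%, 20% and 30% this is 40%, 65%, 89% and 97%. This is the chance that an event occurs, not that it leads to withdrawal.

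**The case against.** The strongest reply is that 7.3 already protects the analysis: a plan that keeps all dosed patients and tests the effect of excluding withdrawals presupposes that their data exist. On that view 4.4.1 is loose wording, meant for patients who withdraw themselves, and 4.4.2 bars contact but not chart review. The study is also a descriptive pilot of 20 patients with no primary safety endpoint and no hypothesis test. This bears on the likely intent and limits the consequences. It does not remove the conflict, because 4.4.1 lists the investigator-directed reasons in the same paragraph and exempts none of them, and 7.3 speaks only of the primary analysis.

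Several stronger readings are tempting, and the documents do not support them:

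- **That the triggering event is erased.** Section 4.4.1 says data will not be collected, not that recorded data are discarded, and 8.2 calls for immediate recording. The event itself may well be captured.
- **That any complication leads to withdrawal.** The reason covers only events that interfere with objectives or evaluation, and it is a listed reason, not an automatic trigger. A stroke or infarction is a study outcome and need not interfere.
- **That methylene blue harms are selectively lost.** G6PD deficiency is an exclusion only when documented in the history (section 4.2), so a deficiency first found after dosing is not clearly a violation. Concomitant medications are checked at Visits 1b and 2. Nothing shows that these violations are the ones likely to surface late, and the exclusions apply to both arms before randomization.
- **That 4.4.1 alone loses delayed hemolysis.** Section 1.5 places it two to five days after the drug, already outside the 90-minute period in section 8.1, although Visit 3 lists adverse event evaluation.
- **That 9.1 directly contradicts 4.4.1.** It governs revoked authorization and bears on investigator withdrawal only by comparison.

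Section 8.1 does allow follow-up to end when a patient is lost, but an inpatient whose record is accessible is not lost in that sense.

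**Conclusion.** The point holds as a contradiction between 4.4.1 and sections 7.3, 8.1 and 8.2 in the current text. If 4.4.1 is the rule that staff follow, at least the data after withdrawal are missing for reasons related to outcome, and the estimates meant to inform a later trial would probably look too favourable.

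The size is about 10 percentage points per lost patient in an arm of 10. This is an illustration, since the number of withdrawals is unknown. Treatment failure is probably the most frequent route, on the assumption that the chart review's 9 of 14 carries over. A difference in loss between arms, including loss of methylene blue harms, is possible but not shown by the documents. No figure stated in the plan changes.

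**What to change.** Amend 4.4.1 to separate the end of participation from the end of data collection, in two cases:

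- **Withdrawal by the investigator of any dosed patient** (adverse event, treatment failure, eligibility violation, noncompliance, other): EHR collection of hemodynamics, adverse events, complications, length of stay and vital status continues on the same schedule as for other dosed patients.
- **Withdrawal of consent or authorization by the patient or the legally authorized representative:** keep the data collected to that point and seek permission for vital status, as section 9.1 already describes for revoked authorization.

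Limit 4.4.2 to the second case, and reconcile both sections with 7.3, 8.1 and 8.2. State whether patients given the other drug under section 3.1, whom that section removes from the comparison, count as withdrawn; 3.1 and 7.3 must also agree on this. Separately, reconcile the 90-minute period in 8.1 with adverse event evaluation at Visit 3, because capture of delayed hemolysis depends on that as well.

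The cost is a protocol amendment, a check that the consent form covers continued chart review, and a little more abstraction for the patients concerned. No new study procedure is needed and clinical care is unaffected.

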3.4 Primary Study Endpoints

The primary endpoint of the study will be the improvement in hemodynamic values as measured by SVR, systemic blood pressure, and amount of vasopressors administered. The monitoring and documentation of hemodynamic values is part of SOC practice during LT surgery.

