7.3 Subject Population(s) for Analysis

Each participant who received the study drug will be included in the primary analysis regardless of study withdrawal for any reason. In the event of any study withdrawals, in secondary analysis we will examine the sensitivity of our results to the exclusion of patients who withdrew.

8 Safety and Adverse Events

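### Section 4.4.1 lets treated patients be withdrawn for treatment failure without data and then replaced, which contradicts the all-treated analysis in section 7.3

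*Combined protocol and SAP*

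**What the plan says.** Section 4.4.1 sets the rule for withdrawn subjects: "No data will be collected for withdrawn subjects. Withdrawn subjects may be replaced during the accrual period". The reasons listed under it include an entry that begins "Treatment Failure: If in the Principal Investigator and/or" and goes on to make the test an investigator's judgment that other treatment was needed. It gives no time point and no SVR limit, and it does not separate dosed from undosed subjects. Section 4.4.2 adds that "no additional attempts will be made to contact the Participant".

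Section 7.3 defines the analysis population: "Each participant who received the study drug will be included in the primary analysis regardless of study withdrawal for any reason". If there are withdrawals, "in secondary analysis we will examine the sensitivity of our results to the exclusion of patients who withdrew". Section 7.2 rules out imputation.

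Section 3.1 deals with rescue at one time only. A patient still vasoplegic 30 minutes after study drug receives the other drug and is left out of the comparison. The frequency of such failures for each drug is then an optional summary. The text of 3.1 has no rule for earlier rescue; a figure in that section is not shown and may cover timing. Section 5.7 confirms that the study is unmasked.

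**The concern.** Sections 4.4.1 and 7.3 cannot both be followed for a patient who was dosed and then withdrawn. Section 7.3 needs that patient's data twice: once to include the patient, and once to see what changes when the patient is left out. Section 4.4.1 says the data will not be collected.

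The reason for withdrawal also matters. Treatment failure is a response to the drug, and it is judged by someone who knows which drug was given. Removing a patient on that ground is informative selection. Replacing the patient refills the arm to 10, so the loss is harder to see and is not corrected.

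Two results are exposed: the hemodynamic summaries that form the primary endpoint (3.4) and the per-drug failure frequency (3.1). Nothing is tested, so type I error and power are not at issue. But 7.1 says the pilot's descriptive data are meant to support the power of a later study, and a biased summary would carry over into that planning.

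**Working it through.** There is no planned figure to reproduce: 7.1 says the existing information does not allow a sample size calculation. The check has two parts.

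**1. The sections side by side.** Let T be the patients who received study drug and W those of them who were later withdrawn.

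- Primary analysis (7.3): population T. Under 4.4.1 there are no values for W, and 7.2 does not impute. The patients contributing values are T without W.
- Sensitivity analysis (7.3): T without W by definition.

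The two sets are identical, so the sensitivity analysis cannot show anything. This needs no assumption about rates.

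**2. How far a failure frequency could move.** Inputs: 10 patients per arm (3.1, 5.2). Assumed, because the documents give no value: 5 of the 10 would have vasoplegia at 30 minutes, and k = 1, 2 or 3 patients are withdrawn for treatment failure and lost.

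- All k would have failed: (5 − k)/(10 − k)
- All k would have recovered: 5/(10 − k)
- Half would have failed: (5 − 0.5k)/(10 − k)

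| k | all would have failed | half | all would have recovered |
|---|---|---|---|
| 1 | 4/9 = 44% | 50% | 5/9 = 56% |
| 2 | 3/8 = 38% | 50% | 5/8 = 63% |
| 3 | 2/7 = 29% | 50% | 5/7 = 71% |

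The direction depends on whether the lost patients would have failed more or less often than the rest of the arm.

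With replacement, let s be the share of treated patients dropped and q the share of those who would have failed. The expected reading is (0.5 − s·q)/(1 − s). For s = 0.1, 0.2 and 0.3 this is:

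- q = 1: 0.4/0.9 = 44%, 0.3/0.8 = 38%, 0.2/0.7 = 29%
- q = 0: 0.5/0.9 = 56%, 0.5/0.8 = 63%, 0.5/0.7 = 71%

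These are the same values, so replacement does not repair the bias.

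For scale, the exact (Clopper-Pearson) 95% interval for 5/10 is 19% to 81%. Every reading above lies inside it.

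**The case against.** The best defence is that 4.4.1 is loosely worded and was never meant to discard data on dosed patients. Several points support this.

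- A sensitivity analysis excluding withdrawals makes sense only if their data are held.
- Section 4.4.2 stops contact only.
- Under 9.1, when authorization is revoked, the investigator "retains the ability to use all information collected prior to the revocation of subject authorization".
- The hemodynamic values exist whatever happens: "The monitoring and documentation of hemodynamic values is part of SOC practice during LT surgery" (3.4), and "The following source data will be directly recorded in the EHR and later retrieved by the study team members" (3.7).
- Record review runs to discharge (6.4), and 9.3 requires missing data to be explained.
- Section 4.4.1 looks like template text: it provides for missed consecutive visits in a study with a single intraoperative dose.
- Consent comes before surgery and not everyone who consents is treated (4.3), so the data and replacement rules could be meant for undosed subjects.

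This makes it less likely that data would be lost in practice, and it is one reason the point is minor. It does not remove the conflict. Section 4.4.1 limits neither rule to undosed subjects or to later data, and two of its reasons, treatment failure and adverse event, arise mainly after dosing. Section 9.1 covers only revoked authorization. No text says how a patient rescued early is counted.

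Three stronger readings are tempting, and the documents do not support them.

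- **That 7.3 itself excludes these patients.** It keeps them. The defect is a contradiction between sections.
- **That the problem is confined to rescue before 30 minutes.** The treatment-failure entry has no time limit, so it reaches rescue at 30 minutes too. There, however, 3.1 is more specific and allows the failures to be counted.
- **That failure will be understated, or one drug favoured.** This requires assuming that only true failures are withdrawn, or that the two arms are withdrawn at different rates. The chart review in 1.3 (9 of 14 with an ineffective response to methylene blue) does not settle it: it used another failure definition and gives no timing.

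**Conclusion.** The point stands as a minor defect. Followed as written, 4.4.1 makes the sensitivity analysis in 7.3 empty and allows response-dependent removal and replacement of treated patients. That conclusion rests on the text alone.

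The size of any bias is not established. The 29% to 71% range rests on an assumed 5/10 and on at most three patients lost. It runs in both directions and lies within the pilot's sampling error. The failure frequency is optional and is not a named endpoint. If only further data were meant to stop, the loss is smaller, but an early-rescued patient still has no counting rule in the text shown.

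A related conflict belongs to the same repair: 3.1 leaves patients rescued at 30 minutes out of the comparison, while 7.3 keeps every treated patient in the primary analysis. Correcting 4.4.1 alone would not make 7.3 workable.

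**What to change.** In 4.4.1:

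- Make treatment failure a reason for rescue and not for withdrawal, and keep these patients' EHR data.
- For dosed subjects who withdraw for other reasons, insert the word *further*, so that only later data collection stops.
- Allow replacement only for subjects withdrawn before study drug.

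In 3.1:

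- Count any rescue with the other drug, before or at 30 minutes, in each arm's failure frequency over all treated patients, and show early rescues separately.
- Replace the exclusion from the comparison with a rule that agrees with 7.3: rescued patients stay in the primary analysis with their data up to rescue.

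The cost is wording in two sections and one eCRF entry for the time and SVR at rescue; SVR is already in the EHR. Clinicians remain free to rescue at any point.

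The downside is small but real. An early rescue is an unblinded decision, and one to three premature switches of would-be responders would turn 5/10 into 6/10, 7/10 or 8/10. Showing early rescues separately lets the reader count them first as non-failures and then as failures, a range of width k/10. That bounds the problem without removing it.
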